## 5.6 Diet/Activity/Other Considerations

### 5.6.1 Diet

Subjects should maintain a normal diet unless modifications are required to manage an AE such as diarrhea, nausea or vomiting.

### 5.6.2 Contraception

Cisplatin is known to be teratogenic and embryotoxic. Pembrolizumab may have adverse effects on a fetus in utero. Furthermore, it is not known if Pembrolizumab has transient adverse effects on the composition of sperm. Non-pregnant, non-breast-feeding women may be enrolled if they are willing to use 2 methods of birth control or are considered highly unlikely to conceive. Highly unlikely to conceive is defined as 1) surgically sterilized, or 2) postmenopausal (a woman who is  $\geq 45$  years of age and has not had menses for greater than 1 year will be considered postmenopausal), or 3) not heterosexually active for the duration of the study. The two birth control methods can be either two barrier methods or a barrier method plus a hormonal method to prevent pregnancy. Subjects should start using birth control from study Visit 1 throughout the study period up to 120 days after the last dose of study therapy.

The following are considered adequate barrier methods of contraception: diaphragm, condom (by the partner), copper intrauterine device, sponge, or spermicide. Appropriate hormonal contraceptives will include any registered and marketed contraceptive agent that contains an estrogen and/or a

progestational agent (including oral, subcutaneous, intrauterine, or intramuscular agents).

Subjects should be informed that taking the study medication may involve unknown risks to the fetus (unborn baby) if pregnancy were to occur during the study. In order to participate in the study they must adhere to the contraception requirement (described above) for the duration of the study and during the follow-up period defined in section 7.2.2-Reporting of Pregnancy and Lactation to the Sponsor. If there is any question that a subject will not reliably comply with the requirements for contraception, that subject should not be entered into the study.

### **5.6.3 Use in Pregnancy**

If a subject inadvertently becomes pregnant while on treatment with Pembrolizumab/Cisplatin, the subject will immediately be removed from the study. The site will contact the subject at least monthly and document the subject's status until the pregnancy has been completed or terminated. The outcome of the pregnancy will be reported to the Sponsor without delay and within 24 hours to the Sponsor if the outcome is a serious adverse experience (e.g., death, abortion, congenital anomaly, or other disabling or life-threatening complication to the mother or newborn).

The study investigator will make every effort to obtain permission to follow the outcome of the pregnancy and report the condition of the fetus or newborn to the Sponsor. If a male subject impregnates his female partner the study personnel at the site must be informed immediately and the pregnancy reported to the Sponsor and followed as described above and in Section 7.2.2.

### **5.6.4 Use in Nursing Women**

It is unknown whether Pembrolizumab is excreted in human milk and there are mixed reports on Cisplatin excretion. Since many drugs are excreted in human milk, and because of the potential for serious adverse reactions in the nursing infant, subjects who are breast-feeding are not eligible for enrollment.

## **5.7 Subject Withdrawal/Discontinuation Criteria**

Subjects may withdraw consent at any time for any reason or be dropped from the trial at the discretion of the investigator should any untoward effect occur. In addition, a subject may be withdrawn by the investigator or the Sponsor if enrollment into the trial is inappropriate, the trial plan is violated, or for administrative and/or other safety reasons. Specific details regarding discontinuation or withdrawal are provided in Section 7.1.4 – Other Procedures.

A subject must be discontinued from the trial for any of the following reasons:

- The subject or legal representative (such as a parent or legal guardian) withdraws consent.
- Confirmed radiographic disease progression
- Unacceptable adverse experiences as described in Section 5.2.1.2

- Intercurrent illness that prevents further administration of treatment
- Investigator's decision to withdraw the subject
- The subject has a confirmed positive serum pregnancy test
- Noncompliance with trial treatment or procedure requirements
- The subject is lost to follow-up
- Administrative reasons

The End of Treatment and Follow-up visit procedures are listed in Section 6 (Protocol Flow Chart) and Section 7.1.5 (Visit Requirements). After the end of treatment, each subject will be followed for 30 days for adverse event monitoring (serious adverse events will be collected for 90 days after the end of treatment as described in Section 7.2.3.1). Subjects who discontinue for reasons other than progressive disease will have post-treatment follow-up for disease status until disease progression, initiating a non-study cancer treatment, withdrawing consent or becoming lost to follow-up. After documented disease progression each subject may be followed by telephone or in person for overall survival until death, withdrawal of consent, or the end of the study, whichever occurs first.

### **5.8 Subject Replacement Strategy**

Patients who are unfit or unwilling to continue study after resection will be replaced. Patients who choose not to undergo surgical resection after initial dose of Pembrolizumab will be replaced. In addition, any patient who does not complete at least 1 week of adjuvant treatment will also be replaced.

### **5.9 Clinical Criteria for Early Trial Termination**

Early trial termination will be the result of the criteria specified below:

1. Quality or quantity of data recording is inaccurate or incomplete
2. Poor adherence to protocol and regulatory requirements
3. Incidence or severity of adverse drug reaction in this or other studies indicates a potential health hazard to subjects
4. Plans to modify or discontinue the development of the study drug

In the event of Merck decision to no longer supply study drug, ample notification will be provided so that appropriate adjustments to subject treatment can be made.

## **6.0 TRIAL FLOW CHART**

### **6.1 Study Flow Chart**

Trial Period:	Screening Phase		Pre-surgery Dose	Surgery	Adjuvant Treatment										End of Treatment	Post-Treatment		
	Pre-screening (Visit 1)	Main Study Screening (Visit 2) P			1	2	3	4	5	6	7	8	9	10	NA	Safety Follow-up n	Survival Follow-Up a	
Treatment Dose Title:			Pre-Surgery Dose P		28 to 77	± 1	± 1	± 1	± 1	± 1	± 1	± 3	± 3	± 3	± 14	Discon		
Scheduling Window (Days):	-35 to -7	-22 to -7	-21 to -7	0												At time of Discon c	30 days and 3 months post discon	+/- 2 weeks
Adjuvant Treatment (Week):					1	2	3	4	5	6	7	10	13	16	19	(20 d )	20 d	
Administrative Procedures																		
Informed Consent	X	X o	X o															
Inclusion/Exclusion Criteria		X																
Demographics and Medical History		X																
Prior and Concomitant Medication Review		X	X		X	X	X	X	X	X	X	X	X	X	X	X	X	X
Pembrolizumab Administration j			X		X		X		X		X	X	X	X				
Cisplatin 40mg/m  weekly if indicated b					X	X	X	X	X	X	X							
Radiation 2-2.2 Gy Fxs M-F					X	X	X	X	X	X	X							

Trial Period:	Screening Phase		Pre-surgery Dose	Surgery	Adjuvant Treatment										End of Treatment	Post-Treatment		
	Pre-screening (Visit 1)	Main Study Screening (Visit 2) P			1	2	3	4	5	6	7	8	9	10	NA	Safety Follow-up n	Survival Follow-Up a	
Treatment Dose Title:			Pre-Surgery Dose P													Discon		
Scheduling Window (Days):	-35 to -7	-22 to -7	-21 to -7	0	28 to 77	± 1	± 1	± 1	± 1	± 1	± 1	± 3	± 3	± 3	± 14	At time of Discon c	30 days and 3 months post discon	+/- 2 weeks
Adjuvant Treatment (Week):					1	2	3	4	5	6	7	10	13	16	19	(20 d )	20 d	
Post-study anticancer therapy status																X		X
Survival Status																X	X	X
Clinical Procedures/Assessments																		
Review Adverse Events		X	X	X	X	X	X	X	X	X	X	X	X	X	X	X	X	
Full Physical Examination e		X														X	X	
Directed Physical Examination					X			X			X	X	X	X			X	
Dental Exam		X h																
Dysphagia/Swallowing Function					X i													
Vital Signs and Weight		X	X		X	X	X	X	X	X	X	X	X	X	X	X	X	

Trial Period:	Screening Phase		Pre-surgery Dose	Surgery	Adjuvant Treatment										End of Treatment	Post-Treatment		
	Pre-screening (Visit 1)	Main Study Screening (Visit 2) P			1	2	3	4	5	6	7	8	9	10	NA	Safety Follow-up n	Survival Follow-Up a	
Treatment Dose Title:			Pre-Surgery Dose P															
Scheduling Window (Days):	-35 to -7	-22 to -7	-21 to -7	0	28 to 77	± 1	± 1	± 1	± 1	± 1	± 1	± 3	± 3	± 3	± 14	At time of Discon c	30 days and 3 months post discon	+/- 2 weeks
Adjuvant Treatment (Week):					1	2	3	4	5	6	7	10	13	16	19	(20 d )	20 d	
ECOG Performance Status		X	X		X			X				X	X	X	X	X		
Laboratory Procedures/Assessments: analysis performed by LOCAL laboratory																		
Pregnancy Test – Urine or Serum -HCG		X																
CBC with Differential m		X		X k	X	X	X	X	X	X	X	X	X	X	X	X		
Comprehensive Serum Chemistry Panel j, m		X		X k	X	X	X	X	X	X	X	X	X	X	X	X		
Urinalysis		X			X			X			X			X		X		
T3, FT4 and TSH		X		X k	X			X			X			X		X		
PT/INR, PTT		X		X k	X			X			X			X		X		
Efficacy Measurements																		
Tumor Imaging f		X													X			

Trial Period:	Screening Phase		Pre-surgery Dose	Surgery	Adjuvant Treatment										End of Treatment	Post-Treatment		
	Pre-screening (Visit 1)	Main Study Screening (Visit 2) P			1	2	3	4	5	6	7	8	9	10	NA	Safety Follow-up n	Survival Follow-Up a	
Treatment Dose Title:			Pre-Surgery Dose P													Discon		
Scheduling Window (Days):	-35 to -7	-22 to -7	-21 to -7	0	28 to 77	± 1	± 1	± 1	± 1	± 1	± 1	± 3	± 3	± 3	± 14	At time of Discon c	30 days and 3 months post discon	+/- 2 weeks
Adjuvant Treatment (Week):					1	2	3	4	5	6	7	10	13	16	19	(20 d )	20 d	
Tumor Biopsies/Archival Tissue Collection/Correlative Studies Blood																		
Archival or Newly Obtained Tissue Collection g		X		X														
Correlative Studies Blood Collection g		X		X k	X		X											

Trial Period:	Screening Phase		Pre-surgery Dose	Surgery	Adjuvant Treatment										End of Treatment	Post-Treatment		
Treatment Dose Title:	Pre-screening (Visit 1)	Main Study Screening (Visit 2) P	Pre-Surgery Dose P		1	2	3	4	5	6	7	8	9	10	NA	Discon	Safety Follow-up n	Survival Follow-Up a
Scheduling Window (Days):	-35 to -7	-22 to -7	-21 to -7	0	28 to 77	± 1	± 1	± 1	± 1	± 1	± 1	± 3	± 3	± 3	± 14	At time of Discon c	30 days and 3 months post discon	+/- 2 weeks
Adjuvant Treatment (Week):					1	2	3	4	5	6	7	10	13	16	19	(20 d )	20 d	

a. Patients will be followed every 3 weeks for first 3 months following CRT (post CRT above) and then every 3 months (every 12 weeks) for first 2 years followed by every 6 months (24 weeks) for a total of 5 years. Adjuvant weeks are numbered starting with first Pembrolizumab infusion which should begin 4-11 weeks after resection. FU visits can be conducted by phone if the study subjects will not see a study doctor on those days.
 
b. Only patients with confirmed high risk features (+ECE and/or + margins) will receive Cisplatin.
 
c. Time of discontinuation is either after last Pembrolizumab dose which will correspond to safety visit at week 20 or at time that patient discontinues treatment due to side effects, progression or withdrawal of consent.
 
d. Safety visit will be completed on week 20 unless study discontinued early at which time it should be done at 30 days post-treatment. 30 day safety follow up visit only needed for subjects who withdraw or discontinue the study.
 
e. Full physical exam only includes full head and neck and fiberoptic exam at week 19 but can be completed between week 11 and 20 to count towards week 19 assessment.
 
f. Pre-operative scans including chest imaging preferably PET/CT and CT neck + contrast. (CT chest and CT neck + contrast would also be acceptable). If contrast contraindicated, MRI of neck is also acceptable. Post CRT imaging requires a PET/CT or CT of neck and chest.
 
g. See procedure manual for tissue specifications and tubes required. MDA fresh tissue to be collected per MDA standard.
 
h. Dental exam to be completed anytime before initiation of radiation.
																		

Trial Period:	Screening Phase		Pre-surgery Dose	Surgery	Adjuvant Treatment										End of Treatment	Post-Treatment		
Treatment Dose Title:	Pre-screening (Visit 1)	Main Study Screening (Visit 2) P	Pre-Surgery Dose P		1	2	3	4	5	6	7	8	9	10	NA	Discon	Safety Follow-up n	Survival Follow-Up a
Scheduling Window (Days):	-35 to -7	-22 to -7	-21 to -7	0	28 to 77	± 1	± 1	± 1	± 1	± 1	± 1	± 3	± 3	± 3	± 14	At time of Discon c	30 days and 3 months post discon	+/- 2 weeks
Adjuvant Treatment (Week):					1	2	3	4	5	6	7	10	13	16	19	(20 d )	20 d	
i. See Table 5 for full list. j. Pembrolizumab to be given 30 minutes before Cisplatin on days administered together. k. To be drawn before surgery (day of surgery or up to 4 days prior acceptable). l. This assessment must be performed prior to the start of radiation treatment. m. For the Radiation and Pembrolizumab arm (intermediate risk), safety labs are not required on non-pembro administration weeks. n. 3 month post-discontinuation visit is highly recommended, but optional. o. Informed consent may be obtained on the same day as screening procedures or on the same day as the pre-surgical pembro dose provided the subject has been given a copy of the consent form in advance of this visit to review or adequate time for review on the same-day has been documented. p. Pre-surgical dose and pre-screening visits may occur on the same day as long as consent is obtained, and eligibility is confirmed prior to pembro dose. All screening labs should be performed within 10 days of treatment initiation (the pre-surgical dose of Pembrolizumab).																		

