## 5.2 Trial Treatments

The treatment to be used in this trial is outlined below in Table 2

Table 2 Trial Treatment

Drug	Dose/ Potency	Dose Frequency	Route of Administration	Regimen/ Treatment Period	Use
Pembrolizumab (Initial infusion)	200 mg	once	IV infusion	Day -21 to -7 (prior to resection)	Experimental
Pembrolizumab	200 mg	Q3W	IV infusion	Day 1 of each 3 week cycle starting 7 days before CRT for 7 doses (including initial dose)	Experimental
Cisplatin	40mg/m2	Weekly	IV infusion	4-8 weeks after resection for 6 doses to begin with radiation	Standard of Care for High Risk only

Radiation	60 Gy	Daily M-F	IMRT	4-8 weeks after resection over 6 weeks	Standard of care
-----------	-------	-----------	------	--	------------------

Treatment will be administered on an outpatient basis. Protocol treatment (pre-surgical Pembrolizumab dose) must begin only after eligibility criteria are confirmed by the UC PI (registration), see study flow for more specific timeframes.

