#### **5.2.2.4 Dose Modification**

##### **5.2.2.4.1 Pembrolizumab - Dose Modification and toxicity management for immune-related AEs associated with pembrolizumab and combination therapy**

Adverse events (both non-serious and serious) associated with Pembrolizumab exposure may represent an immunologic etiology. These adverse events may occur shortly after the first dose or several months after the last dose of treatment. Pembrolizumab must be withheld for drug-related toxicities and severe or life-threatening AEs as per Table 3 below. See Section 5.6.1 and the most current investigator's brochure for supportive care guidelines, including use of corticosteroids.

Table 3

Dose Modification Guidelines for Drug-Related Adverse Events

General instructions:				
Immune-related AEs	Toxicity grade or conditions (CTCAE v 4.0)	Action taken to Pembrolizumab	Immune Related AE management with corticosteroid and/or other therapies	Monitor and follow-up
Pneumonitis	Grade 2	Withhold	
 
Administer corticosteroids (initial dose of 1-2 mg/kg prednisone or equivalent) followed by taper
 
Add prophylactic antibiotics for opportunistic infections
 
	
 
Monitor participants for signs and symptoms of pneumonitis
 
Evaluate participants with suspected pneumonitis with radiographic imaging and initiate corticosteroid treatment
 

	Grade 3 or 4, or recurrent Grade 2	Permanently discontinue		•
Diarrhea / Colitis	Grade 2 or 3	Withhold	
 
• Administer corticosteroids (initial dose of 1-2 mg/kg prednisone or equivalent) followed by taper
 
	
 
• Monitor participants for signs and symptoms of enterocolitis (ie, diarrhea, abdominal pain, blood or mucus in stool with or without fever) and of bowel perforation (ie, peritoneal signs and ileus). Participants with <math>\geq</math> Grade 2 diarrhea suspecting colitis should consider GI consultation and performing endoscopy to rule out colitis.
 
• Participants with diarrhea/colitis should be advised
 

	Grade 4	Permanently discontinue		to drink liberal quantities of clear fluids. If sufficient oral fluid intake is not feasible, fluid and electrolytes should be substituted via IV infusion.
--	---------	-------------------------	--	---

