### **7.2.3 Immediate Reporting of Adverse Events to the Sponsor and to Merck**

#### **7.2.3.1 Serious Adverse Events**

A serious adverse event is any adverse event occurring at any dose or during any use of Merck's product that:

- Results in death;
- Is life threatening;
- Results in persistent or significant disability/incapacity;
- Results in or prolongs an existing inpatient hospitalization;
- Is a congenital anomaly/birth defect;
- Is a new cancer (that is not a condition of the study);
- Is associated with an overdose;
- Is another important medical event

Refer to Table 6 for additional details regarding each of the above criteria.

Any serious adverse event, or follow up to a serious adverse event, including death due to any cause other than progression of the cancer under study that occurs to any subject from the time the consent is signed through 90 days following cessation of treatment, or the initiation of new anti-cancer therapy, whichever is earlier, whether or not related to Merck product, must be reported within 24 hours to the Sponsor and within 2 working days to Merck Global Safety.

Non-serious Events of Clinical Interest will be forwarded to Merck Global Safety and will be handled in the same manner as SAEs.

Additionally, any serious adverse event, considered by an investigator who is a qualified UCCI-HN-15-01 Amendment 17

18MAR2021

physician to be related to Merck product that is brought to the attention of the investigator at any time outside of the time period specified in the previous paragraph also must be reported immediately to the Sponsor and to Merck.

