#### **7.2.3.2 Events of Clinical Interest**

Selected non-serious and serious adverse events are also known as Events of Clinical Interest (ECI). ECIs identified from the date of first dose through 90 days following cessation of treatment, or 30 days after the initiation of a new anticancer therapy, whichever is earlier, must be recorded as such on the Adverse Event case report forms/worksheets and reported within 24 hours to the Sponsor and within 2 working days to Merck Global Safety (Attn: Worldwide Product Safety; [contact]) regardless of attribution to study treatment, consistent with standard SAE reporting guidelines. Events of clinical interest for this trial include:

1. An overdose of Merck product, as defined in Section 7.2.1 - Definition of an Overdose for This Protocol and Reporting of Overdose to the Sponsor, that is not associated with clinical symptoms or abnormal laboratory results.
2. An elevated AST or ALT lab value that is greater than or equal to 3X the upper limit of normal and an elevated total bilirubin lab value that is greater than or equal to 2X the upper limit of normal and, at the same time, an alkaline phosphatase lab value that is less than 2X the upper limit of normal, as determined by way of protocol-specified laboratory testing or unscheduled laboratory testing.\*

**\*Note:** These criteria are based upon available regulatory guidance documents. The purpose of the criteria is to specify a threshold of abnormal hepatic tests that may require an additional evaluation for an underlying etiology. The trial site guidance for assessment and follow up of these criteria can be found in the Investigator Trial File Binder (or equivalent).

1. Additional adverse events:

Subjects should be assessed for possible ECIs prior to each dose. Lab results should be evaluated and subjects should be asked for signs and symptoms suggestive of an immune-related event. Subjects who develop an ECI thought to be immune-related should have additional testing to rule out other etiologic causes. If lab results or symptoms indicate a possible immune-related ECI, then additional testing should be performed to rule out other etiologic causes. If no other cause is found, then it is assumed to be immune-related.

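### SAEs and ECIs are reportable to 90 days after treatment, but no mandatory adverse event assessment is scheduled after about day 28 to 30, so late capture relies on spontaneous reports or an optional visit

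*Combined protocol and SAP*

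**What the plan says.** **The reporting window.** Section 7.2.3.1 requires SAEs to be reported "from the time the consent is signed through 90 days following cessation of treatment", irrespective of relatedness, or until new anti-cancer therapy if that is earlier. Section 7.2.3.2 covers "ECIs identified from the date of first dose through 90 days following cessation of treatment", regardless of attribution, with a shorter limit after new therapy. Sections 5.7 and 7.1.5.3.1 repeat the 90 days for SAEs. Section 5.2.2.4.1 gives the reason for a long window: "These adverse events may occur shortly after the first dose or several months after the last dose of treatment".

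**The schedule.** Footnote d of the flow chart reads "Safety visit will be completed on week 20 unless study discontinued early at which time it should be done at 30 days post-treatment", and adds "30 day safety follow up visit only needed for subjects who withdraw or discontinue the study". Footnote n reads "3 month post-discontinuation visit is highly recommended, but optional". The row "Review Adverse Events" is marked from main screening through the Safety Follow-up column and is blank under Survival Follow-Up.

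**The later contacts.** Section 7.1.5.4 describes the 12-weekly contacts, which may be by telephone, as monitoring for relapse. Section 7.1.5.4.1 describes survival follow-up as assessing survival status. Neither mentions adverse events.

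**Other duties.** Section 7.1.2.1 says adverse events are graded and recorded through the follow-up period. The end of the general text of Section 7.2 says that new events more than 30 days after treatment enter the database only if related to pembrolizumab.

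**The concern.** A duty to report an event helps only if someone learns of it. The protocol sets a 90-day window and itself expects immune-related events months after the last dose. Yet its visit schedule gives no fixed occasion to ask about such events in the later part of that window. Sites that offer the optional visit will find more events than sites that do not, and patients who are well enough to skip it may differ from those who attend.

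The frequency and severity of side effects is the first primary objective (Section 3.1). There is no concurrent control: Section 8.2.4.1 compares grade 3 and 4 rates with fixed historical targets of 39% (radiation) and 50% (chemoradiation). A missed event can lower the observed rate but cannot raise it. With about 40 patients per stratum (Section 8.1.3), each patient whose only grade 3 or 4 event went unrecorded would move that stratum's rate by 1/40 = 2.5 percentage points.

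**Working it through.** The plan gives no figure of its own here, so the check dates the last mandatory review and compares it with the window.

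**Inputs**
- Window: 90 days after cessation of treatment (7.2.3.1, 7.2.3.2).
- Doses: seven at three-week intervals, counting the pre-surgery dose (Table 2, Section 5.2).
- Last mandatory review: week 20 for completers, day 30 for early discontinuers (footnote d; 7.1.5.3.1).
- Follow-up contacts: every 12 weeks, window of plus or minus 2 weeks (flow chart; 7.1.5.4).

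**Step 1, last dose.** Six adjuvant doses from week 1 fall at weeks 1, 4, 7, 10, 13 and 16. The last pembrolizumab mark in the flow chart is also at week 16.

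**Step 2, time without a mandatory scheduled review**, taking cessation as the last dose:
- Completers: (20 − 16) × 7 = day 28; 90 − 28 = 62 days; 62/90 = 69%.
- Early discontinuers: 90 − 30 = 60 days; 60/90 = 67%.

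**Step 3, is the blank cell real?** The chart has 18 columns. The adverse event row is marked in columns 2 to 17. The Survival Status row is marked in columns 16 to 18, so the columns line up and the blank under Survival Follow-Up is not a table-reading error.

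**Step 4, when is the next required contact?** The starting point is not fixed. For completers, in days after the week 16 dose:

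| 12 weeks counted from | Day | With ±2 weeks |
|---|---|---|
| last dose (week 16) | 84 | 70–98 |
| week 19 imaging | (31 − 16) × 7 = 105 | 91–119 |
| week 20 visit | (32 − 16) × 7 = 112 | 98–126 |

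On the last two anchors the contact always falls after day 90. On the first it can be held between day 90 and day 98. One existing contact can therefore cover the whole window by recall.

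**Step 5, other contacts.** Section 2.1 has monthly follow-up for three months after treatment, and footnote a has three-weekly follow-up for three months after chemoradiation. Section 2.1 puts the repeat scan at three months post-treatment, and 7.1.2.6.2 puts that scan 12 weeks after the last radiation, at week 19. Read that way, these contacts end at about week 19, before the gap opens.

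**Step 6, sensitivity to the definition of cessation.** Footnote c links discontinuation to the week 20 visit. If the 90 days ran from week 20, no mandatory review would follow within the window, and the window would end 28 + 90 = 118 days after the last dose.

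**The case against.** The strongest reply is that the flow chart is only a summary, as Section 7.1 says, and that the detailed text does require late events to be captured. Sections 5.7 and 7.1.5.3.1 require SAEs to be collected or recorded for 90 days, 7.1.2.1 has adverse events recorded in follow-up, and Section 7.2 has related events entered after day 30. Medication review is marked under Survival Follow-Up, and 5.4.1 and 7.1.1.4.2 tie late medication records to SAEs and ECIs, so those contacts are not silent on the subject.

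Much of this stands. A reader might infer that the protocol requires no ascertainment at all after week 20; the text does not support that. What the reply does not supply is an occasion to ask. Section 7.1.2.1 has patients assessed at the times set in the flow chart, and more often only where clinically indicated, which leads back to the blank cell. The other sections say what to do with an event once it is known. A medication review may bring an event to light but is not an adverse event review.

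Two further objections stand. The documents give no rate of late events, so the size of any under-count cannot be calculated. The date of the next contact also depends on the anchor, so day 112 is one reading among three.

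**Conclusion.** The point holds in this form: the schedule does not support the 90-day obligation in the text. No mandatory adverse event assessment is scheduled for 60 to 62 of the 90 days (67% to 69%), for any patient in either stratum who is still under observation. Capture in that period depends on spontaneous reports or the optional visit.

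A reader might take the 67% to 69% as the share of late events lost. It is a share of time only; a later contact can recover events by recall, and some will be volunteered. A reader might also conclude that the 3-month visit has to become compulsory. It need not, if an existing contact covers the window.

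Assumptions: cessation of treatment is the last pembrolizumab dose, at week 16 for completers, and no new anti-cancer therapy shortens the window. Dating cessation to week 20 would widen the gap.

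A separate contradiction bears on the same data. Section 7.2 limits new events after day 30 to those related to pembrolizumab, while 7.2.3.1 and 7.2.3.2 require SAEs and ECIs to day 90 whatever their cause. These passages must be reconciled, or sites may leave out reportable events they already know about.

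**What to change.** - In the "Review Adverse Events" row, and in 7.1.5.4 and 7.1.5.4.1, require adverse event review at the first 12-week follow-up contact, with telephone acceptable. Hold it on or after day 90 and ask about SAEs, ECIs and pembrolizumab-related events since the last review.
- Define cessation of treatment and state the point from which the 12 weeks are counted.
- Leave the 3-month visit optional if this contact covers the window.
- Reconcile the relatedness limit in Section 7.2 with 7.2.3.1 and 7.2.3.2.

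The cost is wording changes and a few questions at a contact that already takes place, with no new visit. The limits are some reliance on recall and no help with events found only by blood test: the flow chart schedules no blood tests after the end-of-treatment column, so the laboratory-defined hepatic ECI would still depend on unscheduled testing.
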